4.2 Inclusion criteria

Subjects will be enrolled at Visit 1 (Day 1) if they meet all the following criteria:

- 1. Outsubjects of either sex aged \ge 18 and \le 75 yrs;
- 2. Presence of moderate to severe nasolabials folds (WSRS grade 3-4);
- 3. Reasonable potential benefit from correction;
- 4. Subjects able to understand the full nature and the purpose of the investigation, including possible risks and side effects, able to cooperate with the Investigator and to comply with the requirements of the entire investigation (ability to attend all the planned investigation visits according to the time limits included) based on Investigator's judgement;
- 5. Subjects must voluntarily give written informed consent, adhere to the protocol and report events and concomitant medication for the entire duration of investigation.

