5.2 Dosage and administration

The investigational medical devices must be administered only to subjects selected for taking part in the investigation according to the protocol.

Duration of treatment

Single admnistration of each device (one on right side and the other on the left side of the face).

Dosage and mode of treatment

- study devices will be administered using linear threading, multiple punctate pools, and/or fanlike injection technique. The technique of injectiom and the depth of injection will be at the discretion of the Treating Investigator; however, for a given subject, both devices will be injected at the same depth and with the same technique.
- in all subjects the first injection will be done in the right side of the face, the second in the left side.
- doses: the minimum amount must be at least 0.5 ml per side, the maximum 2 ml per side, per each implant. The Treating Investigator will decide the dose to obtain the optimal correction of defect per each patient implant.

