5.4 Treatment code

A computer-generated randomization list (specifying the type of medical devices to be injected in the right and the left side of the face) will be available.

Each subject included in the investigation will be coded by the Investigator through a 2-digit progressive *Screening number* as they present themselves for the investigation at the screening visit (Visit 1), starting from code 01 preceded by the letter "S" (first subject enrolled: code S01).

If a subject discontinues from the investigation, the screening number will not be re-used, and the subject will not be allowed to re-enter the investigation.

Eligibility confirmed, a randomization number will be done starting from 01 (first subject randomized: code 01).

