Six GAIS forms will be provided for each subject, attached but not included in the CRF.

Clinical efficacy: objective evaluation

The aesthetic results of the treatment will be evaluated by the blind investigator, separately for each site (right/left), by means of the Wrinkle Severity Rating Scale (WSRS)⁴³, based on five scores, done before the treatment and a the weeks 12 and 24:

grade	wrinkle	description
1	absent	no visible nasolabial fold; continuous skin line
2	mild	shallow but visible nasolabial fold with a slight indentation; minor facial feature; implant is expected to produce a slight improvement in appearance
3	moderate	moderately deep nasolabial fold; clear facial feature visible at normal appearance but not when stretched; excellent correction is expected from injectable implant
4	severe	very long and deep nasolabial fold; prominent facial feature; <2 mm visible fold when stretched; significant improvement is expected from injectable implant
5	extreme	extremely deep and long nasolabial fold, detrimental to facial appearance; 2–4 mm visible V-shaped fold when stretched; unlikely to have satisfactory correction with injectable implant alone

The WSRS score will be entered directly in the CRF by the blinded evaluator.

At the final visit both the blind investigator and the subject will express a global satisfaction assessment (GSA) on corrective procedure (for each side of the face):

Global satisfaction assessment	(GSA)) scale
--------------------------------	-------	---------

unsatisfying	satisfying	very satisfying
0	1	2

⁴³ Day DJ, Littler CM, Swift RW et al . *The Wrinkle Severity Rating Scale. A validation study*. Am J Clin Dermatol 2004; 5 (1):49-52

Clinical efficacy: objective recording

Immediately before treatment, after treatment (within 1 hour) and at all follow-up visits (V2-V3-V4) a digital picture of the face will be taken.

The photo will be taken from a frontal point of view according to the standard procedures of the study site (sitting position of the subject; soft environmental daylight; neutral uniform background; digital camera; distance subjects camera 1,2-2.0 m; focal lenght adjusted to 70-90 mm [35 mm format equivalent]; neutral white balance; automatic ISO exposure).

As soon as possible the digital file will be copied in a PC: for each photo almost the date of the shot and the subject number will must available. A separate backup of the files is advisable.

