10.2.1 Sample size

A sample size of 52 subjects achieves 81% power to detect a mean of paired differences of 1.0 with an estimated standard deviation of differences of 2.5 and with a significance level (alpha) of 0.05 using a two-sided paired t-test.

A maximum number of 55 subjects may be recruited to account for a rate of non-evaluable subjects of about 5%

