10.2.5 Statistical methods

Descriptive Statistics:

Descriptive statistics will be provided in summary tables by treatment group according to the type of variable.

Continuous variables will be summarized by number of observations, mean and standard deviation, median, minimum, and maximum. Categorical variables will be summarized using counts of subjects and percentages.

All data collected will be presented in the listings.

Subject accountability:

Disposition of subjects, subject status and subjects excluded from different analysis sets will be summarized.

Baseline characteristics:

Demographic and baseline characteristics will be summarized by means of descriptive statistics. No formal statistical tests will be performed to verify the homogeneity of the sequence groups at baseline visit (intra-subjects study).

Performance endpoints

Primary performance endpoint will be the mean pain score experienced by the subject in the first hour after each treatment. The pain measurement will be obtained from the VAS scores. Based on these VAS scores, the area under the curve from treatment until 1 hour after will be calculated and this area under the curve will be divided by time. This resulted in a mean VAS score that will be compared between treatment with a paired t-test.

For secondary endpoint a two-sided Wilcoxon signed-rank test will be done.

Safety endpoints

AEs which occurred before and those which started after the application of the investigational device (treatment-emergent AEs, TEAEs) will be presented separately.

All AEs will be tabulated by System Organ Class (SOC) and Preferred Term (PT) after medical coding using the most recent MedDRA thesaurus version. The primary SOC and the PT will be used for the analysis of the frequency distribution in the two groups.

The number of TEAEs (i.e. AEs started after the start of treatment), treatment-emergent SAEs, TEAEs related to the medical device under investigation, treatment-emergent SAEs related to the medical device, and the number and proportion (with exact 95% CI) of subjects with at least one TEAE, treatment-emergent SAE, TEAE related to the medical device and treatment-emergent SAEs related to the medical device will be presented by treatment group.

The incidence of TEAEs in the two treatment groups will be compared by means of McNemar test.

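### The plan gives the side-specific Visit 1 WSRS grade no role in the HAL v HA comparison; adjusting for it would protect power at almost no cost

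*Combined protocol and SAP*

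**What the plan says.** The whole inferential text for the secondary endpoints is one sentence, in Section 10.2.5 and again in the Protocol Summary: "For secondary endpoint a two-sided Wilcoxon signed-rank test will be done". It does not name the variable, the week or any covariate, and it has to serve GAIS, WSRS and the satisfaction rating together.

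Of these, only WSRS has a pre-treatment value. Section 7 has the blinded evaluator grade each side separately, with the scale "based on five scores, done before the treatment and a the weeks 12 and 24"; the schedule in Section 6 agrees (Visits 1, 3 and 4). GAIS is already scored relative to the pre-treatment state, and satisfaction is recorded only at the final visit.

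Entry requires "Presence of moderate to severe nasolabials folds (WSRS grade 3-4"), with no requirement that the two sides match. Section 5.4 allocates device to side from a computer-generated list. The plan mentions change from baseline only for vital signs (Sections 8 and 10.2.5). Section 10.2 defers full methods to a detailed SAP to be issued before database lock.

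**The concern.** In a split-face design the natural quantity is the within-subject HAL minus HA difference in grade. If only follow-up grades enter it, a subject who started at grade 3 on one side and 4 on the other may still show part of that difference at week 12 or 24 for reasons unrelated to the device. Randomising the side makes this average out across subjects, but it inflates the variance of the paired difference.

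Comparing the efficacy of the two devices is a stated secondary objective (Section 2.2), and Section 1.2 itself raises reduced efficacy or durability as a concern when lidocaine is added. Lower power makes a real loss easier to miss. The value needed to remove the noise is already collected at Visit 1.

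**Working it through.** **The plan's own figure.** Section 10.2.1 states: "A sample size of 52 subjects achieves 81% power to detect a mean of paired differences of 1.0". Its other inputs are 2.5 for the SD of those differences and a paired t-test at the two-sided 5% level. The noncentrality is (1.0/2.5) × √52 = 2.88 on 51 degrees of freedom, which gives 80.8% power and agrees with the stated 81%. Also 52/0.95 = 54.7, so 55 recruited. Both reproduce, but they concern pain. No power, effect size or standard deviation is stated for WSRS.

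**Model for WSRS.** Let D be the HAL minus HA grade difference within a subject:

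D_post = δ + b × D_base + e, with SD(e) = s

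- a: share of subjects with a one-grade difference at entry. D_base is then −1, 0 or +1, with variance a under randomised sides. One grade is the maximum if the 3–4 criterion applies to each side; the text does not say so explicitly.
- b: fraction of the entry difference that persists to follow-up.
- s: residual SD of the between-side difference, taken as 0.7 grade.

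All of a, b and s are assumptions. The variance of the paired quantity is:

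- follow-up only: b²a + s²
- change from baseline: (1 − b)²a + s²
- baseline-adjusted: s² (apart from the cost of estimating one slope)

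Change therefore beats follow-up only when (1 − b)² < b², that is, when b > 0.5.

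**Power at n = 52.** Set δ so that the adjusted analysis has 80% power: δ = (1.960 + 0.842) × 0.7/√52 = 0.272 grade. Power is then Φ(δ/√(variance/52) − 1.960).

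Example, a = 0.2 and b = 1, follow-up only: variance = 0.20 + 0.49 = 0.69; standard error = √(0.69/52) = 0.115; 0.272/0.115 − 1.960 ≈ 0.40; power 65.6%.

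Follow-up only / change from baseline, in % (adjusted is 80.0 in every cell):

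| a | b = 0.25 | b = 0.5 | b = 0.75 | b = 1 |
|---|---|---|---|---|
| 0 | 80.0 / 80.0 | 80.0 / 80.0 | 80.0 / 80.0 | 80.0 / 80.0 |
| 0.1 | 79.5 / 75.6 | 78.0 / 78.0 | 75.6 / 79.5 | 72.3 / 80.0 |
| 0.2 | 79.0 / 71.4 | 76.1 / 76.1 | 71.4 / 79.0 | 65.6 / 80.0 |
| 0.3 | 78.5 / 67.6 | 74.2 / 74.2 | 67.6 / 78.5 | 59.7 / 80.0 |
| 0.5 | 77.5 / 60.8 | 70.6 / 70.6 | 60.8 / 77.5 | 50.4 / 80.0 |

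At b = 0 the follow-up-only variance is s², so nothing is lost. At a = 0.2 the loss from ignoring baseline therefore runs from 0 to 80.0 − 65.6 = 14.4 points. At a = 0.5 and b = 1 it is 80.0 − 50.4 = 29.6 points.

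**Check on discrete grades.** Grades were rounded and limited to 1–5, with a latent effect of 0.3 grade, per-side error SD 0.45, n = 52 and 2,000 simulated trials per cell. The signed-rank test was used for follow-up and change, and the t-test of the intercept for the adjusted analysis.

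| a | b | Follow-up only | Change | Adjusted |
|---|---|---|---|---|
| 0.2 | 0.25 | 79.0% | 71.7% | 78.4% |
| 0.2 | 0.5 | 75.4% | 75.2% | 78.0% |
| 0.2 | 0.75 | 72.1% | 77.4% | 77.8% |
| 0.2 | 1 | 64.8% | 78.6% | 77.7% |
| 0.4 | 0.25 | 77.4% | 66.6% | 79.2% |
| 0.4 | 1 | 56.6% | 79.8% | 78.8% |

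Without asymmetry the three agree (78% to 82%). Under no effect (a = 0.2, b = 0.75, 4,000 trials) the rejection rates were 5.2%, 5.0% and 4.9%. Only the adjusted analysis holds its power across the grid.

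**The case against.** The strongest reply is that the plan has not decided anything here. A reader might infer that it rejects baseline and tests follow-up grades only. The documents do not support that: the sentence leaves the variable unnamed, a signed-rank test on each side's change from Visit 1 would fit it equally well, and a detailed SAP is promised. This stands, so the finding is that baseline has no stated role, not that it has been excluded. The promise of a SAP does not remove the gap; it is the place to close it, before WSRS results are seen.

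The loss may also be small. Entry is limited to two adjacent grades, and Section 5.2 says "The Treating Investigator will decide the dose to obtain the optimal correction of defect per each patient implant". If a deeper fold receives more filler, less of the entry difference may persist. This stands too, and it is why the size is shown over a range of b.

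A reader might also infer that a signed-rank test on change from baseline is the obvious cure. That holds only if more than about half of the entry difference persists, and nothing in the documents establishes this. At 20% asymmetry and b = 0.25, change has 71.4% power against 79.0% for follow-up only.

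Finally, the efficacy measures in Section 2.2 are listed without a hierarchy, so WSRS cannot be called the main secondary question. Reading a non-significant difference as equal efficacy would be an error under any of these tests; baseline adjustment does not turn a difference test into evidence of equivalence.

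**Conclusion.** The point holds as an inexpensive improvement to a secondary analysis. The plan collects side-specific WSRS at Visit 1 and assigns it no role in the HAL v HA comparison. If follow-up grades alone are tested, the cost depends on how many subjects enter asymmetric and how much of that persists: none without asymmetry, about 0 to 14 points of power at 20% asymmetric, and up to about 30 points at 50% with full persistence. These figures assume a between-side residual SD of 0.7 grade, 52 evaluable subjects and 80% power for the adjusted analysis; the documents supply only the 52.

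A reader might infer bias, or damage to the trial's main result. Neither follows. Side is randomised, type I error stays near 5% whichever analysis is used, and the pain endpoint with its stated 81% power is unaffected.

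**What to change.** State in the SAP, before any WSRS results are seen, that at each of weeks 12 and 24 the lead WSRS analysis is a linear regression of the within-subject HAL minus HA difference in grade on the HAL minus HA difference at Visit 1. The intercept, reported with its 95% CI, is the device difference for a subject whose two sides started equal. If no subject is asymmetric at entry, the slope drops out and the analysis becomes the mean paired difference.

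Keep the two-sided Wilcoxon signed-rank test as the supporting analysis and name the variable it uses. Do not make a signed-rank test on change from baseline the lead.

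The cost is a sentence or two in the SAP and no new data. The downside is negligible: one degree of freedom, and a linear model applied to an ordinal grade, for which the retained signed-rank test is a check.

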Primary performance endpoint will be the mean pain score experienced by the subject in the first hour after each treatment. The pain measurement will be obtained from the VAS scores. Based on these VAS scores, the area under the curve from treatment until 1 hour after will be calculated and this area under the curve will be divided by time. This resulted in a mean VAS score that will be compared between sequence with a paired t-test.

For secondary endpoint a two-sided Wilcoxon signed-rank test will be done.

Safety endpoints

AEs which occurred before and those which started after the application of the investigational device (treatment-emergent AEs, TEAEs) will be presented separately. All AEs will be tabulated by System Organ Class (SOC) and Preferred Term (PT) after medical coding using the most recent MedDRA thesaurus version. The primary SOC and the PT will be used for the analysis of the frequency distribution in the two groups. The number of TEAEs (i.e. AEs started after the start of treatment), treatment-emergent SAEs, TEAEs related to the medical device under investigation, treatment-emergent SAEs related to the medical device, and the number and proportion (with exact 95% CI) of subjects with at least one TEAE, treatment-emergent SAE, TEAE related to the medical device and treatmentemergent SAEs related to the medical device will be presented by treatment group. The incidence of TEAEs in the two sequence groups will be compared by means of McNemar test. Risk ratios and odds ratios with 95% CIs, Fisher's exact test and logistic regression will be considered to compare proportions between treatment groups. The results of changes from baseline in vital signs (blood pressure and heart rate) will be presented as descriptive statistics.

Starting and ending date

AS CONSEQUENCE OF THE ONGOING COVID 19 PANDEMIC, SEVERAL ACTIVITIES (SOCIAL, ECONOMICS AND HEALTHCARE) ARE DELAYED OR STOPPED. THEREFORE, TO HYPOTHESIZE THE ACTUAL TIMES OF THE STUDY IS DIFFICULT. AS SUPPOSITION, MAY BE THAT THE STUDY WILL START (FIRST PATIENT IN) DURING THE FIRST HALF YEAR 2021 AND WILL END (LAST PATIENT OUT) DURING THE FIRST HALF YEAR 2022.

Matex Lab Switzerland

CONFIDENTIAL

LIST OF ABBREVIATIONS

ADE	Adverse Device Effect
AE	Adverse Event
ASADE	Anticipated Serious Adverse Device Effect
ATC	Anatomical Therapeutical Classification
BDDE	Butane Diol Diglycidyl Ether
CE	Communauté Européenne
CI	Confidence Interval
CIR	Clinical Investigation Report

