2.2 Secondary objectives

The secondary objectives of this investigation are:

- To assess and compare the safety of HAL and of HA;
- To assess and compare and the efficacy of HAL and of HA injection. Clinical efficacy will be determined by the
 - Global Aesthetic Improvement Scale (GAIS), done by the subject at weeks 2, 12 and 24;
 - Wrinkle Severity Rating Scale (WSRS), done by the blinded evaluating investigator at weeks 12 and 24;
 - o blinded evaluating investigator and subject satisfaction done at week 24;
 - o digital photography done before treatment and at weeks 2, 12 and 24.

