3. INVESTIGATION DESIGN

This will be a pre-CE mark controlled, prospective, randomized, blinded evaluator, single centre, split-face clinical investigation.

Each subject will receive both medical devices under investigation, one (HAL) on the one side of the face, the other (HA) on the other side, in randomized fashion.

The products will be administered by the Investigator/Co-Investigator (Treating Investigator), while the evaluations will be done by a Co-Investigator not aware of the side type treatment (Blinded Evaluator).

The investigational plan include a Visit 1, during which subjects will be screened for entry (inclusion/exclusion) criteria; eligible subjects will be treated with the medical devices and followed for the next hour for pain and safety evaluation.

Visit 2, 3 and Visit 4 are schedule after 2 (\pm 2 days), 12 (\pm 10 days) e 24 (\pm 10 days) weeks for the assessment of safety and clinical efficacy.

Subjects prematurely discontinued from the investigation after the treatment will perform an 'Early termination visit', in which procedures scheduled for Visit 4 (24 weeks, final visit) will be performed (whenever feasible). In case of premature discontinuation of the investigation, the Investigator will duly record the reason for premature withdrawal in the appropriate section of the case report form (CRF).

Visit 4 (or the 'Early termination Visit') will represent the conclusion of subject's participation in the investigation.

Adverse events will be recorded during the entire investigational period by investigator's assessment and subjects' spontaneous reporting. Vital signs (blood pressure and heart rate) will be measured at each visit in the investigational site.

The total duration of the investigation for each subject will be 24 weeks. This time frame has been selected basing on literature data related to dermal fillers based on hyaluronic acid.

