8. ASSESSMENT OF SAFETY

The safety endpoints of this investigation will be:

- Incidence of local and systemic adverse events;
- Changes from baseline in vital signs (blood pressure and heart rate).

Methods of assessment

Adverse events

Definitions, coding, methods of collection of adverse events and medical device incidents are described in details in Section 9.

Vital signs

Vital signs will be recorded at each investigation visit.

Systolic and diastolic blood pressure will be measured in sitting position after at least 5 minutes rest. Heart rate will be measured for one minute just prior to the sitting blood pressure measurement.

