9.4 Follow-up of adverse events

Complete and accurate data on all AEs experienced for the duration of the reporting period will be reported on an ongoing basis in the AE forms of the CRF.

It is important that each AE report include a description of the event, its expectedness, whether it is considered serious, its duration (onset and resolution dates), its intensity, its relationship to the medical device, any other potential causality factors, any action taken and its outcome.

Note: After completion of the investigation the Sponsor will continue to have an obligation to report serious and treatment-related AEs affecting the investigation subjects.

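### The plan tests HAL against HA on all TEAEs, but in a split-face subject a systemic event cannot be assigned to one device, and the side of a local event is not a required entry

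*Combined protocol and SAP*

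**What the plan says.** Section 2.2 makes a between-device comparison a secondary objective: "To assess and compare the safety of HAL and of HA". Section 8 defines the safety endpoint as "Incidence of local and systemic adverse events", together with vital signs.

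Section 3 gives the design: "Each subject will receive both medical devices under investigation". Sections 5.2 and 6.1 place both single administrations at Visit 1, right side first and then left.

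Section 10.2.5 defines a TEAE only by its start after treatment. It presents TEAEs, serious TEAEs and device-related TEAEs by treatment group, and then says: "The incidence of TEAEs in the two treatment groups will be compared by means of McNemar test". The synopsis has the same sentence for different groups: "The incidence of TEAEs in the two sequence groups will be compared by means of McNemar test". Neither place separates local from systemic events, and no section says how an event without a side is allocated to HAL or HA.

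On collection, Section 9.4 asks that "each AE report include a description of the event, its expectedness, whether it is considered serious, its duration", and goes on to intensity, relationship to the medical device (in the singular), other causes, action taken and outcome. Side of face is not listed. Section 9.2 has the Investigator collect events by spontaneous report, observation and open questions.

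**The concern.** McNemar's test needs a yes or no for each device in each subject. For a systemic event this design cannot supply that pair of answers. Both devices are in the same person from the same visit, so neither site nor onset date separates them.

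Such events are foreseeable. Section 1.4 lists light-headedness, circumoral numbness, double vision and tinnitus as early signs of lidocaine toxicity. Only one of the two devices contains lidocaine, so an assessor who assigns such a complaint to a device has an obvious candidate.

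For local events the design does work, provided the side is known. The protocol requires a separate record for each side for VAS, GAIS, WSRS and the global satisfaction assessment (Section 7), but not for adverse events. At stake is whether the comparative safety objective yields a result that reflects the devices or one that reflects an unstated allocation rule.

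**Working it through.** The plan gives no figure for the TEAE comparison. Its one power figure, 81% with 52 subjects, concerns the pain endpoint. It reproduces at 80.8% (paired t-test, difference 1.0, SD 2.5, two-sided alpha 0.05) and has no bearing here. Only the denominators 52 and 55 (Section 10.2.1) are taken from the plan. **All event counts below are assumptions**, because the documents give none.

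**Test.** Let b be the subjects with a TEAE under HAL only, and c those with a TEAE under HA only. The exact two-sided McNemar p is 2 × Σ C(b+c, i) × 0.5^(b+c), summed over i from 0 to min(b, c), capped at 1. Concordant subjects do not enter.

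**What allocation does to one subject's pair**
- Counted under both devices, a subject with no other TEAE becomes concordant, and the test does not move.
- Counted under both, a subject with a local TEAE on one side only changes from discordant to concordant. A real local difference is then hidden.
- Counted under one device, a subject with no other TEAE becomes a discordant pair created by attribution.
- A subject who already has local TEAEs on both sides is unaffected by any rule.

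**Illustration with local events present.** Assume 52 subjects: 10 with local TEAEs on both sides, 6 on the HAL side only and 8 on the HA side only. Add 10 subjects whose only TEAE cannot be assigned.

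| Rule for the 10 subjects | b v c | Subjects with a TEAE, HAL v HA | Exact p |
|---|---|---|---|
| Left out | 6 v 8 | 16 v 18 | 0.79 |
| Counted under both | 6 v 8 | 26 v 28 | 0.79 |
| All to HAL | 16 v 8 | 26 v 18 | 0.15 |
| All to HA | 6 v 18 | 16 v 28 | 0.023 |

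With 5 such subjects, the last two rows give p = 0.65 (11 v 8) and p = 0.17 (6 v 13).

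**Dilution of the risk ratio.** With assumed counts of 16 v 24, the ratio is 16/24 = 0.67. Counting 10 more subjects under both devices gives 26/34 = 0.76.

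**The extreme case.** Six systemic complaints all assigned to HAL, with no other discordant subject, give p = 2 × 0.5^6 = 0.031; 5 v 0 gives 0.0625. One HA-only subject changes 6 v 0 to 6 v 1, and p = 2 × (1 + 7)/128 = 0.125. Added to local discordance of 6 v 8, the same six give 12 v 8 and p = 0.50.

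**Incidence.** Six events counted under both devices raise each incidence by at most 6/52 = 11.5 points, or 6/55 = 10.9 with 55 subjects. The full rise occurs only if none of the six already had a TEAE, because the table counts subjects with at least one.

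**The case against.** A reader might infer that the AE report records no side. The documents do not show that. The AE form is not among them, Section 9.4 lists what a report should contain rather than specifying a form, and the description of the event may carry the location. What can be said is that the protocol does not require the side.

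A reader might also infer that an unblinded investigator will push systemic events towards HAL. Section 3 assigns evaluations to a co-investigator who is unaware of the side. Against that, Section 9.2 gives AE collection to the Investigator without naming the Blinded Evaluator, and the Treating Investigator consults the randomisation list and handles boxes that show the product (Sections 5.3 and 6.1). Unblinded attribution is therefore possible, but not established.

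Nor do the figures predict a false positive. The 6 v 0 case needs no discordance at all in the other direction, yet Section 1.4 calls local reactions such as bruising and erythema the most common events. It also says that low lidocaine doses are generally well tolerated.

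Finally, Section 10.2 promises a detailed SAP before database lock, which could set the rule for which events enter the comparison. That is a fair answer on the analysis. It does not answer the rest: a later SAP cannot recover a side that was never collected, and no rule can make a systemic event attributable to one of two devices given at the same visit.

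**Conclusion.** The concern holds for systemic events whatever the AE form looks like. The stated analysis puts them into a HAL v HA comparison for which the design gives no valid per-device outcome. For local events it holds in a weaker form: the protocol does not guarantee that they can be traced to a device, and how many would be untraceable is unknown.

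The size cannot be derived from the documents. Under the assumed counts above, the choice of rule alone moves p between 0.023 and 0.79, but most of the allocations tried do not reach 0.05. The 11.5-point rise is an upper bound.

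A secondary objective is affected; the primary pain comparison is not. The point should be settled before enrolment, because the side of an event is hard to recover reliably afterwards.

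**What to change.** 1. **Section 9.4 and the AE form:** add a mandatory field with the options right, left, both, or not side-specific.
2. **Section 10.2.5 and the synopsis:** restrict the by-device tables and the McNemar test to side-specific local TEAEs. Link each event to the device actually injected on that side, using the product label stuck in the CRF (Section 6.1, treatment procedure), not the randomisation list, so that a swapped side is classified correctly. Report systemic TEAEs once per subject for the combined procedure, with no HAL v HA test. Align the synopsis with Section 10.2.5 at the same time: the comparison is between treatments within subjects, whereas sequence groups are different subjects and are not paired.
3. **Section 2.2, or the analysis text:** state that the comparative safety objective applies to local events and that systemic safety is described overall.

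The cost is one tick-box on a paper form and a few sentences. The downside is that no comparative claim on systemic safety can be made, but the design cannot support one in any case.
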